11.0 Statistical/Data Analysis Plan

11.1 Statistical Considerations:

List the statistical methods to be used to address the primary and secondary objectives, specific aims, and/or research hypotheses. Explain how missing data and outliers will be handled in the analysis. The analysis plan should be consistent with the study objectives. Include any sub-group analyses (e.g., gender or age group). Specify statistical methods and variables for each analysis. Describe how confounding variables will be controlled in the data analysis

The statistical plans discussed below are not final or definitive. They will need to evolve as the flu seasons develop and we communicate with other ILI study centers and the sponsors. In case of

a severe epidemic, they may have to change substantially. Detailed statistical protocols will need to be created for the specific studies that will fulfill secondary objectives. The statistical considerations below for the secondary objectives will serve as starting points for the more detailed statistical plan.

Primary Aim

Specific Aim #1: Comparison of the effectiveness (prevention of laboratory-confirmed influenza illness) of three types of licensed seasonal influenza vaccines.

Research question: Is either the cell-culture based vaccine or the recombinant vaccine more effective than egg-based vaccine? There are two hypotheses of interest based on influenza attack rates (AR): Vaccine Effectiveness (VE)= $(\underline{AR}_0 - \underline{AR}_1) \times 100\% = (1-\underline{AR}_1/\underline{AR}_0) \times 100\% = (1-\underline{RR}) \times 100\%$

AR₀

when AR_0 is placebo, VE~= vaccine efficacy or via Nauta ("absolute vaccine efficacy") when AR_0 is the egg-based vaccine then the VE~= *relative* vaccine efficacy.

We want relative VE of 33% => $1 - AR_1/AR_{egg} = 0.33$, therefore 1- 0.33 = $AR_1/AR_{egg} = RR$ therefore 0.67 =RR (AR1 = attack rate in either cell-culture based or recombinant vaccine)

We have simplified the primary hypotheses for the study and have opted for two pairwise comparisons rather a single three-way comparison. There are two hypotheses of interest based on influenza attack rates (AR):

H₀: RR=1 vs H_A: RR < 1; alpha=0.025;

The RR to be tested is defined as: 1) RR1=AR_{cell} / AR_{egg} and 2) RR2=AR_{recombinant} / AR_{egg} Text: Statistics in Clinical Vaccine Trials by Jozef Nauta.

1. Endpoint:

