Specific Aim #4: To evaluate the association host single nucleotide polymorphisms (SNPs) on the immune responses to the influenza vaccine and on influenza severity

Endpoints:

- Frequency of SNPs by seroconversion status
- Frequency of SNPs by geometric mean titer (GMT) cutoff
- Frequency of SNPs by mean fold rise (MFR) cutoff
- Frequency of SNPs by influenza status
- Frequency of SNPs by influenza severity classification

11.2 Sample Size:

18000

11.3 Total number of subjects requested (including records and specimens):

18000

11.4 If you are recruiting by study arm, please identify the arms of the study and how many subjects will be enrolled in each arm

Arm 3: egg-based influenza vaccine, 6,000.

Sub-study: Approximately 1,200 subjects total recruited from the main study population.

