4.1.2 Immune Response

- 4.1.2.1 Hemagglutination inhibition (HI) titers for A/H1N1, B/Yamagata, and B/Victoria
- 4.1.2.2 Microneutralization (MN) titers for influenza A/H3N2

4.1.2.3 Seroconversion Rate (SCR): Proportion of study participants with either a pre-vaccination titer <10 and a post-vaccination titer \geq 40, or a pre-vaccination titer \geq 10 and a \geq 4-fold increase in post-vaccination titer

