4.1.2.4 Geometric mean titers (GMT)

4.1.2.5 Mean-fold rise (MFR): (post-sample / pre-sample) vaccination titers

4.1.3 Other

4.1.3.1 Laboratory-confirmed influenza hospitalization

Laboratory-confirmed influenza as determined by RT-PCR from nasopharyngeal swab specimens collected upon presentation with ILI and hospitalized within *14* days of laboratory confirmed influenza.

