5.2.2 Endpoints

5.2.2.1 Relative risk for seroconversion

Relative risk of seroconversion among participants who received cellculture-based influenza vaccine (FlucelvaxR) as compared to those receiving egg-based influenza vaccine will be calculated using the following formula:

$$RR_{cell} = \frac{p_{cell}}{p_{egg}}$$

Where:

 p_{cell} = proportion seroconvert among the cell-culture-based influenza vaccination group

 p_{egg} = proportion seroconvert among the egg-based influenza vaccination group

and

Relative risk of seroconversion among participants who received recombinant HA (FluBlokR) influenza vaccine as compared to those receiving egg-based influenza vaccine will be calculated using the following formula:

$$RR_{recombinant} = \frac{p_{recombinant}}{p_{egg}}$$

Where:

 $p_{recombinant}$ = proportion seroconvert among the recombinant HA influenza vaccination group

 p_{egg} = proportion seroconvert among the egg-based influenza vaccination group

The proportion that seroconvert equals the number seroconvert (definition 3.1.2.3) divided by the number of vaccinated individuals that were enrolled in the Sub-Study and had the pre- and post-blood draws.

Confidence intervals (95%) will be calculated using the standard formulas for relative risk. The relative risk will be statistically significant if the p-value is less than or equal to 0.025 (one-sided test). The interim analysis for relative risk after the first influenza season uses a stricter p-value (<0.0001). Because of this, the final analysis will not need to adjust the p-value out of concerns about multiple looks.

Relative risk for seroconversion as defined in 5.2.2.1 will be evaluated for each vaccine-type (A/H1N1, B/Yamagata, B/Victoria, and A/H3N2);

5.2.2.2 Geometric Mean Titers (GMTs) – GMTs will be calculated pre- and post-vaccination. Non-inferiority will be based on a 2-sided test comparing post-vaccination GMTs between vaccine types.

5.2.2.3 Mean-Fold Rise – Ratios of participant post-vaccination titers divided by the pre-vaccination titers.

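### Exploratory Aim 4 relates SNPs to immune response through unstated cutoffs on titre and fold rise; a regression on each subject's log titre would define the endpoint and normally keep more information

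*Protocol*

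**What the plan says.** Protocol 9.4 and Protocol 11.1 both list, under Specific Aim 4, "Frequency of SNPs by geometric mean titer (GMT) cutoff" and "Frequency of SNPs by mean fold rise (MFR) cutoff". Neither place states the value of a cutoff, the antigen, the assay, the sampling time or the method of analysis.

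The two lists differ in their first item. Section 11.1 begins with "Frequency of SNPs by seroconversion status". Section 9.4 begins with influenza status and severity and does not list seroconversion, so there the two cutoffs are the only immune-response endpoints for this aim.

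The SAP does not fill the gap. Its exploratory objectives (2.3) and its other analyses (5.3) do not mention SNPs; section 3.2 mentions only the optional buccal swab. It does show how the two quantities are understood:

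- **GMT** (SAP 5.2.2.2) is a summary used for "comparing post-vaccination GMTs between vaccine types".
- **MFR** (SAP 4.1.2.5 and 5.2.2.3) is defined in the latter as "Ratios of participant post-vaccination titers divided by the pre-vaccination titers".
- **Seroconversion** (SAP 4.1.2.3) is a defined yes/no status for each participant: a titre below 10 rising to at least 40, or a titre of at least 10 rising at least four-fold.

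Protocol 11.1 opens with the caveat that "The statistical plans discussed below are not final or definitive".

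**The concern.** There are two separate problems.

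The first is definition. No individual has a geometric mean titre, so the GMT endpoint cannot be computed unless it is read as each subject's own titre cut at some value. Even then the value is open. SAP 2.2 names four vaccine components, and Protocol 11.1 (SA 2.2) uses two assays, so there are many possible versions and nothing prevents a choice after the data are seen.

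The second is efficiency. Titre and fold rise are graded measurements. Reducing either to above or below a cut normally costs power. This applies to MFR as well, although MFR is well defined for a person.

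The endpoint lists also name no adjustment. Protocol 11.1 (SA 2.5) itself says that prior vaccination and infection affect the response, and race and ethnicity are collected at enrolment (Protocol 10.1). Allele frequencies can differ by ancestry, and so may titres, so a SNP comparison that ignores ancestry can mislead.

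**Working it through.** **No stated figure to reproduce.** The documents give no sample size, power or cutoff for Aim 4. The nearest figure is the sub-study size in Protocol 11.5: 50% seroconversion against 50% × 1.22 = 61%, one-sided alpha 0.025, power 0.80.

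n per arm = [1.960 × √(2 × 0.555 × 0.445) + 0.842 × √(0.50 × 0.50 + 0.61 × 0.39)]² / 0.11² = 319.2, so 320.

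With 20% loss, 320 / 0.80 = 400 per arm, or 1,200 in all. This agrees with the protocol. It sizes the comparison of seroconversion between arms, not the genetic analysis.

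**Information kept after a split.** Assume a continuous, normal log titre and a small additive effect. For a cut with fraction q above it, the efficiency relative to a linear analysis is φ(z_q)² / [q(1 − q)].

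| Cut | Calculation | Kept | Lost |
|---|---|---|---|
| Median, q = 0.50 | 0.3989² / 0.25 | 0.637 | 36.3% |
| Quartile, q = 0.25 | 0.3178² / 0.1875 | 0.539 | 46.1% |
| Top tenth, q = 0.10 | 0.1755² / 0.09 | 0.342 | 65.8% |

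**In subjects.** The number with both paired titres and an opt-in swab is not given. The rows below assume full swab uptake; at uptake u, multiply by u.

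| Base | Source | Median split | Quartile split |
|---|---|---|---|
| 1,200 | Protocol 11.5, no loss | 764 | 646 |
| 1,020 | 1,200 × 0.85 | 649 | 549 |
| 960 | 1,200 × 0.80 | 611 | 517 |
| 1,000 | SAP 3.2, no loss | 637 | 539 |

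**In power.** A two-sided 5% test with 80% power on the continuous titre has a standardised effect of 1.960 + 0.842 = 2.802. After a median split this becomes 2.802 × √0.637 = 2.235, and the power is Φ(2.235 − 1.960) = 61%. Simulation with an assumed allele frequency of 0.3 gave 60% to 62% for a median split and 52% to 56% for a cut at the 75th percentile. Restoring 80% after a median split needs 1 / 0.637 = 1.57 times as many subjects.

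**How far the 36% depends on normality.** The documents give no titre distribution. Smallest losses under other assumptions:

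- Titres read in two-fold steps, log2 SD 1.0 to 2.5, no censoring: 31.0% to 35.5%.
- The same, censored two steps below the median: 27% to 30%; censored one step below: about 18%.
- Logistic log titres, median split: 18% against a comparison of means, 25% against a rank test.
- Laplace log titres, median split: no loss against a comparison of means (relative efficiency 2.0 in favour of the split).

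**The case against.** The strongest reply is that this is an endpoint list for an exploratory aim in a plan that calls itself provisional. It states no test, so silence on adjustment is not a decision to compare crude frequencies. That stands, and it keeps the severity low. It does not supply the missing definition: the later detailed protocols promised in 11.1 are for the secondary objectives, and Aim 4 is exploratory.

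Several stronger readings are tempting, and the documents do not support them:

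- *Neither GMT nor MFR exists for an individual.* True of GMT only. The SAP defines MFR as a participant's own ratio, so an MFR cutoff can be applied to a person.
- *At least 36% of the information is lost.* This is the normal-theory loss at the median, not a floor. Two-fold steps, censoring or heavier tails can bring it lower.
- *The effective sample is 764 or 646.* Those values assume that all 1,200 are genotyped and complete both draws. The actual base is not stated.
- *Arm could confound the SNP comparison.* Vaccine is randomised and genotype is fixed beforehand, so arm can be associated with genotype only by chance. Adjusting for arm serves precision. Ancestry is the real confounder.
- *The aim cannot afford the loss.* No power target, effect size or sample size is set for Aim 4, so this cannot be shown.

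One technical reply also has weight. Adjusting for pre-vaccination titre is a choice of estimand, because genotype may have shaped earlier responses. The adjusted model asks about response given the starting titre, which fits an aim about response to the vaccine, but the protocol should say so.

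**Conclusion.** The point holds as a low-severity improvement. The GMT endpoint has no individual-level meaning as written, both cutoffs are undefined, and splitting titre or fold rise normally gives up information that the study will already have collected. The size is about 36% at a median split and about 46% at a quartile split if log titres are roughly normal and the SNP effect is small; it may be less on real assay data. In subjects this is about 764 of 1,200 at a median split under full genotyping and completion, about 611 of 960 after 20% loss, and proportionately fewer with incomplete swab uptake. The primary and secondary aims are unaffected.

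**What to change.** In Protocol 9.4 and 11.1, replace the two cutoff endpoints with one regression per antigen, naming the assay:

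- Outcome: each subject's log2 post-vaccination titre.
- Exposure: allele count.
- Adjustment: log2 pre-vaccination titre, and race/ethnicity to address confounding by ancestry.
- Arm and season: included for precision.
- Repeat enrolment: Protocol 12.1 lets earlier subjects enrol again, so use one record per person or standard errors clustered on the subject. Otherwise the same genotype is counted as independent evidence more than once.

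Use seroconversion status, as defined in SAP 4.1.2.3, as the single binary version. It is already in 11.1 and must be added to the list in 9.4. State the number of subjects with both paired titres and a swab when it is known.

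The cost is protocol wording and a standard regression on data already planned. No new samples or visits are needed.

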11.5 Please provide a justification for your sample size

Main Study

Based on an alpha of 0.025 (1-sided) and a power of 0.80, a sample size of 18,000 (6,000 per arm) subjects has the power to detect a 33% difference in effectiveness between egg-based vaccine and two other vaccine preparations, assuming an influenza incidence of 2.3% in the egg-based arm and 1.54% in the cell-culture-based and recombinant arms. It assumes that 15% of subjects will be lost to follow-up.

Substudy

Based on an alpha of 0.025 (1-sided) and a power of 0.80, a sample size of 1,200 subjects (400/arm) has the power to detect a 22% relative difference in seroconversion rate if there is a 50% seroconversion at day 28 among the egg-based vaccine recipients. It assumes that 15-20% of subjects will be lost to follow-up.

11.6 Data Analysis Plan:

See section 11.1

12.0

Participant Information

12.1 Subject Population:

The study is comprised of DEERS-eligible adults (active duty, retirees and beneficiaries) vaccinated (at an MTF) (will be vaccinated) with one of the licensed egg-based, cell-culture-based or recombinant influenza vaccines during the 2018-2019, 2019-2020, 2020-2021, 2021-2022 influenza seasons in the United States. Subjects enrolled in the study during 2018-2019, 2019-2020, and/or 2020-2021 may also be enrolled in the 2021-2022 season.

12.2 Age Range:

Check all the boxes that apply. if the age range of potential subjects (specimens, records) does not match the range(s) selected, please specify in the text box.

0-17

- ✓ 18-24
- 25-34
- 35-44
- 45-54
- 55-64
- 65-74
- 75+

12.3 Gender:

- Male
- ✓ Female
- C Other

12.4 Special categories, check all that apply

- Minors /Children
- ✓ Students
- Employees Civilian
- Employees Contractor
- Resident/trainee
- Cadets /Midshipmen
- Active Duty Military Personnel
- Wounded Warriors
- Economically Disadvantaged Persons
- Educationally Disadvantaged Persons
- Physically Challenged (Physical challenges include visual and/or auditory impairment)
- Persons with Impaired Decisional Capacity
- Prisoners
- Pregnant Women, Fetuses, and Neonates
- Non-English Speakers
- International Research involving Foreign Nationals Headquarters Review is necessary

You must also consider the requirements of DoDI 3216.02, Enclosure 3, paragraphs 7.e. and 12.

You must also consider the requirements of DoDI 3216.02, Enclosure 3, paragraph 7.e.

12.5 Inclusion Criteria:

Order Number	Criteria
1	Eligible for care in DoD facilities (DEERS eligible)
2	Greater than or equal to 18 years of age
3	At a participating MTF site for the purpose of receiving a seasonal influenza vaccination.
4	Able to speak English and able to provide informed consent
5	Able to receive and respond to texts and/or emails, or a military recruit

12.6 Exclusion Criteria:

Order Number	Criteria
1	Adults intending to receive or who have received the current season's FluMist vaccine (LAIV).
2	Adults who have already received a Flu Vaccine within the current season
3	Individual who cannot receive a flu vaccine or standard dosing due to another medical condition
4	Allergic to gentamicin, polymyxin, and/or neomycin
	Individuals who fail to meet the inclusion criteria

13.0

Recruitment and Consent

13.1 Please describe the recruitment process, including how subjects will be identified and selected for the study.

Identification and Selection of Subjects:

Potential subjects may be encouraged using recruitment flyers that may be posted at the sites in areas such as acute care clinics, ward workrooms, the emergency room, the commissary, the post exchange and/or base exchange and outside MTFs (e.g. shipyard, military bases, branch clinics etc.) as appropriate (if accessible at the MTF (i.e., MAMC). Print advertisements may be placed in the command newspaper at each participating MTF. Sites may choose to disseminate the flyer via email to targeted audiences (e.g. house staff/attending physicians) or via the web using social media networks (i.e. Facebook). In addition, a recruitment poster/flyer may be provided to patients during intake by clinic staff to inform potential enrollees about the study. All advertisements will include information summarizing the study enrollment criteria, dates and locations for enrollment, and indicate that participation in research is voluntary.

All recruitment material will be reviewed and approved by the IRB prior to use.

Eligibility Assessment Process:

Any person eligible to receive care at one of the participating DoD inpatient facilities or outpatient clinics, and who meets all inclusion criteria and exclusion criteria is eligible for participation in the study. Eligibility for care is determined by the Defense Enrollment Eligibility Reporting System (DEERS). This will include individual active duty service members, retired military, and their eligible dependents. Attempts will be made to enroll subjects of all genders and racial and ethnic origins. Coordinators will confirm DEERS eligibility based on CAC, military identification and military health care documents.

Recruitment Process:

Electronic Enrollment:

Potential subjects can be sent consents, educational and recruitment material via email 30 days prior to vaccination day up to two times prior to vaccination day.

E-consent links and QR codes will be given via email or in-person for potential subjects to sign up for the study. Subjects will receive a screening questionnaire and instruction sheet to ensure they understand the procedures, are eligible for the study, and have contact information for the staff if they have questions.

In-person recruitment:

Recruitment and consent in the MTFs may take place up to 30 days prior to randomization and vaccination. Research protocol briefs may be given on a regular basis by the site PIs or a member of the study team to training programs and to the inpatient/outpatient health care staff in their primary care clinics as well as the emergency room staff. Following the medical briefing, a study investigator will give a 10-minute briefing that outlines the proposed research study. No officers in the chain of command will be present during the briefing or the consent process. It will be made clear during the briefing that enrollment is completely voluntary and that enrolling, or failing to enroll, will in no way affect their standing. Any healthcare worker who was not present at the briefing, will be given the opportunity to participate once they have received study information and are given the opportunity to ask questions.

After the investigator's briefing, there will be a 10-minute period (more time will be allowed if needed) for any questions potential subjects may wish to ask publicly. They will also be given the opportunity to ask additional questions in private. Questions on the nature of the study, the means by which it is to be accomplished, and the risks to the subjects will be addressed. Any questions that cannot be answered will be referred to the site PI. No study procedures will occur prior to the subject giving informed consent.

Active duty members

Recruitment and enrollment of active duty members in groups, may take place outside MTFs (e. g. military units, shipyard, etc.), or at command briefings for recruits. Following the medical briefing, a study investigator will give a 10-minute briefing that outlines the proposed research study. No officers in the chain of command will be present during the briefing or the consent process. It will be made clear during the briefing that enrollment is completely voluntary and that enrolling, or failing to enroll, will in no way affect their standing.

Beneficiaries

Prior (via electronically) or when beneficiaries arrive at the MTF (in person) to receive their influenza vaccination, the immunization or study staff are able to make beneficiaries aware of the study and may provide them with recruitment materials describing the study. Individuals who are interested learning more about the study will be directed to speak with a study staff team member. Beneficiaries will be given the opportunity to ask questions in private. Questions on the nature of the study, the means by which it is to be accomplished, and the risks to the subject will be addressed. Any questions that cannot be answered will be referred to the site PI. No study procedures will occur prior to the subject giving informed consent.

Immunogenicity Substudy: Substudy participants are recruited from subjects enrolled in the main study. Participation in the main study is a requirement for substudy enrollment. The study team will focus on recruitment and enrollment into the immunogenicity sub-study in the weeks preceding the start of vaccination. The recruitment strategy for the sub-study will be similar to the main study utilizing a combination of flyers, outreach in MTF clinics to target beneficiaries, group briefings for MTF health care works and offsite military units (e.g. sailors assigned to ships in dry dock, trainees at the Medical Education and Training Campus (METC), etc). Using a similar recruitment and enrollment strategy to the main (VE) study will allow for a similar composition of subjects between the sub-study and overall cohort. Subjects recruited during the 'prevaccination window' will be enrolled and complete the pre-vaccination blood draw, and then return for randomization and vaccination at the 'vaccination or Day 0' visit. Once the sites start vaccination visits, recruitment and enrollment efforts will prioritize the main (VE) study, although sites can continue enrollment in the immunogenicity sub-study in order to meet enrollment targets. Enrollments into the immunogenicity sub-study will be stratified by site but not by any other parameters (e.g. day of week, every 3rd enrollment etc). Of note, individuals must be enrolled in the main study (VE) in order to participate in the sub-study. Individuals who agree to participate in the sub-study will be required to complete the main study consent document (PAIVED ICD) in addition to the sub-study consent document (PAIVED Sub-Study ICD).

13.2 Compensation for Participation:

FLUPRO Questionnaire:

Subjects who develop ILI symptoms will receive \$10 for their best effort in completing the 7 day entries, at the ILI Visit 1.

Blood Collection:

- \$10 per self-collected blood sample
- \$50 per venipuncture

Under 24 USC 30, payment to Federal Employees and Active Duty military personnel for participation in research while on duty is limited to blood donation and may not exceed \$50 per blood draw. They may not receive any other payment or non-monetary compensation for participation in a research study unless they are off duty or on leave during the time they are participating in the protocol.

Nasal swab:

Individuals will be compensated \$10 per each of the nasal specimens.

Participants may be compensated for up to three new ILI episodes per season. ILI episodes must be separated by at least 30 days. Recruits/trainees may be compensated if permitted per

military policy. In the event that a mitra kit or self-collected nasal swab is collected by a subject but the study staff does not receive it a subject may be compensated and can be compensated for a replacement.

13.3 Please describe the pre-screening process. If no pre-screening, enter Not Applicable in the text editor

For potential subjects who a e-consenting, there will be a pre-screen eligibility questionnaire.

13.4 Consent Process:

Are you requesting a waiver or alteration of informed consent?

• Yes • No

What type?

Waiver of documentation of informed consent

Waiver or alteration of informed consent

Please explain why your study is eligible for the requested waiver

We are requesting an alteration of informed consent to a short form consent. Since we are looking to enroll a very large sample during a very short time, use of a short form consent will make the consent process more efficient, thereby giving staff members more time to answer any questions that the subjects may have. The short informed consent has all of the required elements.

Please explain the consent process:

ICD and Assent Regulatory Requirements:

The Informed Consent Document (ICD) will be reviewed and approved by the IRB prior to initiation of the study. The ICD Form contains a full explanation of the possible advantages, risks, and alternatives to participation, and availability of treatment in the case of injury.

An ICD, in compliance with applicable DoD regulations, 32 CFR 219, the Belmont Principles, the Health Insurance Portability and Accountability Act (HIPAA) Authorization, and California Subject' s Bill of Rights (if applicable) will be signed by the subject or representative before any study-related procedures are initiated for each subject. The investigator will retain the ICD and authorization form as part of the study records. Only PIs, research physicians, clinical coordinators, research assistants, and site managers listed in Personnel and Collaborators Protocol Attachment will present the protocol in lay terms to the subjects. As part of the informed consent process, study staff will describe study procedures, risks of the study, and alternative to participation to the potential subject either in person or electronically. All subjects will be given the opportunity to ask questions. Any question that cannot be answered by the study staff will be referred to the principal investigator (PI) and/or research physicians. Study staff will make all effort to answer questions to the subjects to satisfaction prior to granting consent. Informed consent includes the principle that it is critical the subject be informed about the potential risks and benefits. This information will allow the subject to make a personal risk versus benefit decision and understand the following general principles:

- a. Participation is entirely voluntary,
- b. Subjects may withdraw from participation at any time,
- c. Refusal to participate involves no penalty, and
- d. The individual is free to ask any questions that will allow him/her to understand the nature of the protocol.

Study staff will clearly state that enrollment in the study is completely voluntary. At the end of the discussion, all subjects will be provided an electronic copy or the paper consent form, the HIPAA authorization form, and the California Subject's Bill of Rights (if applicable) to carefully read and review before considering whether or not to participate.

Should the protocol be modified, the subjects consent document will be revised, as needed, to reflect the changes to the protocol. If the subject is directly affected by the change, and it is directed by the IRB, each subject will be re-consented per the previously defined process and

subjects will be offered a copy of the newly signed and dated ICD. The approved revision will be read, signed, and dated by the subject subjects.

Informed Consent Process - Enrollment

In response to a flyer or other print advertisement, a potential subject may call the study coordinator for more information regarding the study. The study coordinator will explain the study and/or ask the individual or group to come to the MTF for further discussion and possible enrollment. Following the recruitment procedures, those interested subjects will be offered the consent form and authorization forms to sign or paper or electronically. In accordance with DoD regulations, if a military member is interested in volunteering, their informed consent process will not take place in the presence of uniformed personnel in their chain of command or in the presence of a superior officer. At the time of consent, HIPAA authorization will also be obtained.

Study staff will be available to answer any questions an individual may have before deciding whether or not to participate in the study. When each individual has determined that they are interested in participating, they will sign the appropriate consent form in front of the designated study staff (listed in the Personnel and Collaborators Attachment). Each subject will have the ability to opt-in for a buccal swab and for same-day/post-vaccination self-collected blood samples. Subjects will elect to opt into this procedure in a designated area of the consent form and will do so without penalty or loss of entitlements. A copy of the signed ICD will be offered to the subject and the original document will be retained by the investigative team.

A subject is considered to be enrolled when they have signed a consent form and HIPAA authorization form (and California Bill of Rights, if applicable).

Substudy enrollment:

Study staff listed in the Personnel and Collaborators Attachment will ensure that each potential enrollee of the substudy is presented with the Substudy ICD. This ICD will be explained by the consenting study staff member and the potential participant will be able to ask any questions they may have. If a subject chooses to participate, the substudy ICD will be signed after the main ICD is completed and before any substudy procedures are done. Substudy participants will be offered a copy of their signed substudy ICD.

Participation Log

If individuals agree to participate, identifiers and the study ID, will be recorded in the participation log on a secure computer. Completed study procedures will be documented in the electronic participation log.

13.5 DoDI 3216.02 requires an ombudsman to be present during recruitment briefings when research involves greater than minimal risk and recruitment of Service members occurs in a group setting. If applicable, you may nominate an individual to serve as the ombudsman.

🖸 N/A

Propose ombudsman

13.6 Withdrawal from Study Participation:

Explain the process for withdrawal and specify whether or not the subjects will be given the opportunity to withdraw their data their data/specimens in the event they wish to withdraw from the study

A subject may voluntarily end participation in the study at any time. If a subject withdraws, the investigator will make a reasonable effort to determine the reason for the subject's withdrawal from the study. Telephone calls, registered letters, and/or e-mail correspondence will be considered reasonable effort for subjects whom are deemed lost to follow up. "Lost to follow-up" is defined as a subject who **enrolled in the study and** received a randomly allocated vaccine but did not respond to any ILI surveillance, or a subject who reported ILI symptoms but then did not complete any ILI visit or ILI-related procedures.

Subjects who withdraw because of study-related AEs will be followed to resolution of AE or as long as reasonably possible. In the event of a continuing study-related AE, the information will be provided to the Institutional Review Board (IRB).

For the immunogenicity sub-study, "lost to follow-up" is a sub-study subject who did not complete the two blood draws and will be reported to the IRB during continuing review. All data and specimens collected up to the time of withdrawal will be reported and retained.

14.0

Risks and Benefits

14.1 Risks of Harm:

Identify all research-related risks of harm to which the subject will be exposed for each research procedure or intervention as a result of participation in this study. Consider the risks of breach of confidentiality, psychological, legal, social, and economic risks as well as physical risks. Do not describe risks from standard care procedures; only describe risks from procedures done for research purposes

FDA-approved influenza vaccines are made by a number of manufacturers and are classified as either "live attenuated" or "inactivated" influenza vaccines. This study will compare the relative effectiveness of three inactivated influenza vaccine formulations, an egg-based, a cell-culture-based, and a recombinant. The live attenuated vaccine (i.e. Flumist) will not be evaluated in this study. There are 3 separate egg-based vaccines being studied. To date, there is no published data to suggest that there are "clinically significant" differences in the rate of adverse events following immunization (AEFI). The CDC/ACIP's current guidance to providers is to administer any licensed, age-appropriate influenza vaccine with no preference expressed for one vaccine over another. Active duty members are required to receive an annual influenza vaccination and voluntary for retirees and beneficiaries. Approximately 90% of active duty members and healthcare workers and 40% of beneficiaries are vaccinated each season.

We contend that the PAIVED study meets the standard for a minimal risk study for the following reasons: the Centers for Disease Control and Prevention (CDC) and its Advisory Committee on Immunization Practices (ACIP) recommend that all patients 6 months of age and older be vaccinated annually against influenza. Moreover, the ACIP's current guidance to providers is to administer any licensed, age-appropriate influenza vaccine (Inactivated influenza vaccines (IIV), Recombinant influenza vaccine (RIV), or live attenuated influenza vaccine (LAIV4) with no preference expressed for one vaccine over another (Appendices 2-4). A summary of the common adverse effects following immunization (AEFI) associated with influenza vaccines to be used the study is presented in Appendix 5. To date, there no published data to suggest that there are "clinically significant" differences in the rate of adverse events following immunization (AEFI) with the various products and no nationally authoritative body has seen a need to preferentially avoid one vaccine's side effects for another product. Thus, it is well within the standard of care to give any patient any of the FDA-approved vaccines. It should be noted that among the products to be administered have different excipients (Fluarix contains gentamicin and Afluria contains neomycin and polymyxin) so participants with who are allergic to these medications would have an increased risk of an adverse event, consequently, allergies to gentamicin, neomycin and polymyxin has been added to the study exclusion criteria.

This **comparative effectiveness study** is designed to follow individuals who have allocated to receive one of three FDA licensed types influenza vaccine formulations in order to evaluate their relative impact of on risk of influenza acquisition and immune responses. Given that all the vaccines represent the standard of care and will be administered in accordance with ACIP recommendations, to those who are not allergic to vaccine components, the only increased risk to subjects in the study would be related to the risk of a blood draw (syncope, bruise, etc.) as well as any remote risk of PII compromise.

1. Rare (Event rate < 1%)

- Secondary infection and syncope from vasovagal reactions occur from blood collection in rare cases. Nasal swabs could trigger symptomatic nose bleeds in rare cases.
- 2. Less Likely (1% greater or equal Event Rate 5%)
 - Nasal swabs may abrade or irritate mucosal surfaces already inflamed due to respiratory infections, leading to discomfort and minimal local bleeding.

- 3. Likely (5% greater or Equal Event Rate < 5%)
 - Bruising and bleeding may occur as a result of blood collection procedure. Nasal swabbing for viral diagnostics and cheek swabbing for obtaining shed buccal cells (for future study of genetic polymorphisms) may cause local discomfort.
- 4. More likely (Event rate less or equal to 10%)
 - No known risks

1. Risk of Phlebotomy

The primary risks of phlebotomy include local discomfort, occasional bleeding or bruising of the skin at the site of needle puncture, and rarely hematoma, infection, or fainting. At the time of enrollment and at Day 21-35, each subject in the immunogenicity substudy will be asked about participation in other research studies to ensure that blood draws do not exceed the following amounts for all research protocols combined: 10.5 mL/kg or 550 mL, whichever is smaller, over any 8-week period for adults. Subjects will also be asked to collect a minimal amount of blood for both ILI visits along with an opt-in pre and post vaccination using a small finger prick.

For assessment of risk in this class of subjects we look to the DHHS IRB Guidebook Chapter VI – Special Classes of Subjects. Section B of that chapter speaks to the risk of phlebotomy in pregnant women:

Obtaining this modest phlebotomy and nasal specimens from pregnant women should conform to the specific requirements of 45 CFR 46, section 207.

2. Risk of Nasal and Buccal Specimen Collection

Nasal swabbing for pathogen diagnostics may cause brief, local discomfort. While less likely, obtaining a nasal swab may trigger sneezing, coughing, or a gag reflex, which is slightly more likely in subjects who are already suffering from these symptoms. Rarely, nasal swabs could trigger a symptomatic nosebleed.

Cheek swabbing for obtaining shed buccal cells (for future study of genetic polymorphisms) may cause local discomfort.

Any adverse event resulting from blood collection procedures will be managed according to standard clinical procedures.

3. Confidentiality Breach

